***Date of signature indicates date of approval**

Acknowledged By Sponsor:

14SEP2020

[figure not shown]
Name and Title (Print)

Signature of Sponsor

Date

GLAUKOS CONTACT INFO

Sponsor:

Chief Medical Officer:

Study Manager:

Table of Contents

1	INTRODUCTION	9
2	OBJECTIVE	10
3	STUDY DESIGN	10
3.1	Discussion of Study Design	11
4	STUDY MEASURES.....	11
4.1	Efficacy Measures	11
4.2	Safety Measures	12
4.3	Other.....	12
5	MATERIALS	12
5.1	Study Medications.....	12
6	METHODS	13
6.1	Subjects	13
6.2	Eligibility Requirements	14
6.3	Procedures	18
6.4	Concomitant Therapies	22
6.5	Post-Treatment Management of IOP and Rescue Medications	22
7	EXTENT OF EXPOSURE AND TREATMENT COMPLIANCE	23
8	STATISTICAL ANALYSES	23
8.1	Sample Size.....	23
8.2	Analysis Populations	23
8.3	General Statistical Methods	23
8.4	Efficacy Analyses.....	23
8.5	Safety Analyses	24
8.6	Interim Analyses	24
9	ADVERSE EVENTS	24
9.1	Serious Adverse Event	26
9.2	Unexpected Adverse Event	27
9.3	Suspected, Unexpected, Serious, Adverse Reaction (SUSAR)	28
9.4	Adverse Events Follow-up	28
10	MAINTAINING THE MASK.....	28
11	INFORMED CONSENT	28

12	INSTITUTIONAL REVIEW	28
13	CONFIDENTIALITY/PUBLICATION OF THE STUDY	28
14	STATEMENT OF COMPLIANCE	29
15	RECORD KEEPING	29
15.1	Source Documents.....	29
15.2	Data Collection.....	30
15.3	Study Supply Accountability	30
15.4	Record Retention.....	31
16	REFERENCES	32

List of Figures

Figure 1.	Glaukos Travoprost Intraocular Implant	12
Figure 2.	Glaukos Travoprost Intraocular Implant and Inserter	13

List of Appendices

APPENDIX A:	SCHEDULE OF VISITS AND MEASUREMENTS	33
APPENDIX B:	OBLIGATIONS OF THE INVESTIGATOR.....	34

SYNOPSIS

This prospective, non-randomized, open-label, multi-center, single arm, clinical trial intends to exchange the implant in approximately █ male and female subjects who were previously implanted with the Travoprost Intraocular Implant in the GC-009 study (1st Cycle). All subjects are required to meet eligibility criteria at Visit 1 (Screening). The purpose of this study is to evaluate the safety of the exchange of a Travoprost Intraocular Implant in subjects with a previously implanted Travoprost Intraocular Implant. Postoperatively, there are 6 follow-up visits over a 12 month period.

Test Article(s): Travoprost Intraocular Implant, [REDACTED]

STUDY OBJECTIVE

The study objective is to evaluate the safety of the surgical exchange procedure of Travoprost Intraocular Implant in subjects with a previously implanted Travoprost Intraocular Implant.

STUDY TREATMENTS

Subjects will undergo an exchange of a Travoprost Intraocular Implant through a small temporal clear corneal incision.

Structure: Single arm

Number of Centers: Approximately 15 centers

Masking: Open-label

Method of Subject Assignment:

After Visit 1 (Screening), qualified subjects will be scheduled to undergo treatment with the G2TR-█ implant.

Randomization: No

Total Sample Size: Approximately [REDACTED] subjects

Statistical Rationale Provided: Please refer to Statistical Section, [Section 8](#)

STUDY OVERVIEW

Subjects will be assessed for inclusion/exclusion criteria at Visit 1 (Screening). At this visit, all subjects must meet all entry criteria. Subjects who meet criteria at Visit 1 (Screening) may be scheduled for Visit 2 (Operative Exchange Day 0) (on a separate day).

Visit Schedule:

This study will consist of 8 visits over approximately a 12 month period: Visit 1 (Screening), Visit 2 (Operative Exchange Day 0), Visit 3 (Day 1 Post-Exchange), Visit 4 (Day 10 Post-Exchange), Visit 5 (Week 4 Post-Exchange), Visit 6 (Month 3 Post-Exchange), Visit 7 (Month 6 Post-Exchange), and Visit 8 (Month 12 Post-Exchange).

Study Measures will be collected for the study eye only:

Safety

- Intra-operative adverse events
- Post-operative adverse events
- Corrected visual acuity (logMAR score using ETDRS chart)
- Slit-lamp biomicroscopy findings
- Gonioscopy findings
- Specular microscopy findings
- Intraocular Pressure
- Ophthalmoscopy findings
- Visual field evaluation

Other

- Operative and surgical assessments

Specified Plan for Data Analysis: Yes (refer to [Section 8](#))

Power and Sample Size: The sample size of [REDACTED] who undergo an exchange of a Travoprost Intraocular Implant was determined empirically. This sample size is considered adequate to support the objective of this study.

STUDY VARIABLES AND STATISTICAL ANALYSIS

Efficacy Variable

There is no efficacy variable in this study. Intraocular pressure is assessed for safety.

Safety Variables

Adverse events (intra-operative and post-operative [TEAEs]) in the study eye will be monitored and summarized.

Ocular safety variables, i.e., best spectacle corrected visual acuity, biomicroscopy findings, gonioscopy findings, specular microscopy findings, intraocular pressure, ophthalmoscopy findings (including cup-to-disc ratio), and visual field evaluation, will be summarized.

Analysis Populations

All subjects who undergo the exchange procedure will be included in the safety population. The safety population will be used for all data tabulations and listings.

LIST OF ABBREVIATIONS AND DEFINITION OF TERMS

Abbreviation/Term	Definition
α -agonists	α -adrenergic receptor agonists
AC Tap	Anterior Chamber Aqueous Humor Sample
AE	Adverse Event
BAK	Benzalkonium chloride
β -blockers	β -adrenergic receptor antagonists
BSCVA	Best Spectacle Corrected Visual Acuity
CAI	Carbonic Anhydrase Inhibitor
CRF	Case Report Form
ETDRS	Early Treatment of Diabetic Retinopathy Study
FDA	Food and Drug Administration
GCP	Good Clinical Practice
IOP	Intraocular Pressure
IEC	Independent Ethics Committee
IRB	Institutional Review Board
ITT	Intent-To-Treat
LogMAR	Logarithm of the Minimum Angle of Resolution
MA	Medical Affairs
MedDRA	Medical Dictionary for Regulatory Activities
mmHg	Millimeters of mercury
OAG	Open-angle glaucoma
OHT	Ocular hypertension
PAS	Peripheral Anterior Synechia
PE	Post-Exchange
PGA	Prostaglandin Analogue
PP	Per protocol
SAE	Serious Adverse Event
SAP	Statistical Analysis Plan
TEAE	Treatment Emergent Adverse Event
VA	Visual acuity

1 INTRODUCTION

Glaucoma is a group of eye diseases characterized by progressive, irreversible and largely asymptomatic vision loss caused by optic nerve damage, which is most commonly associated with elevated levels of intraocular pressure.

Glaucoma is a chronic condition that progresses slowly over long periods of time and can have a devastating impact on a patient's vision and quality of life. Reducing intraocular pressure currently is the only proven treatment for glaucoma.

Treatment for open-angle glaucoma (OAG) traditionally has started with topical ocular hypotensive medical therapy. Development of more effective medications has increased the popularity of this approach as initial treatment compared to more invasive incisional or drainage device surgery.

Furthermore, the more benign medication treatments preserve the ocular tissues in the event that more invasive surgical approaches are eventually required.

The various topical ocular medications available to reduce IOP include miotics, β -adrenergic receptor antagonists (β -blockers), carbonic anhydrase inhibitors (CAIs), α -adrenergic receptor agonists (α -agonists), and prostaglandin analogues (PGAs). The PGAs are a class of ocular hypotensive agents that have been proven effective in lowering IOP in subjects with OAG or OHT. Other advantages of this class of medications is that the systemic side effects associated with α -agonists (e.g., dry mouth, drowsiness) and β -blockers (e.g., depression, fatigue, bradycardia) do not appear to be associated with PGAs. Furthermore, the ocular side effects typically associated with α -agonists (e.g., allergic reactions), and cholinergic agents (e.g., reduced vision), do not seem to manifest with the use of PGAs.

However, PGAs have been shown to be associated with side effects such as ocular hyperemia, iris hyperchromia, periorbital atrophy, increased eyelash growth, general ocular surface discomfort and headache.¹⁻⁵ These side effects and other factors including cost, compliance, and the difficulty of proper instillation, can sometimes hinder the proper use of topical medications.^{6,7} Some patients may possess or develop an intolerance to topical medications or the preservatives in their formulations.

The Travoprost Intraocular Implant was developed to remove or minimize the issue of patient compliance with topical hypotensive medication. This clinical protocol will evaluate the second cycle of the Travoprost Intraocular Implant: Model G2TR-█.

This implant has the potential for providing important benefits to patients. The long duration of drug therapy provided by the implant avoids the problem of compliance with topical ocular hypotensive medications. In addition, the small clear corneal incision required for implantation and the minimally

invasive implant size avoids some of the complications of more invasive surgical procedures for treating glaucoma.

Model G2TR-[REDACTED] has been investigated in clinical trials conducted in [REDACTED] (Phase 1/2) as well as the United States (Phase 2 and Phase 3). The results from the U.S. Phase 2 trial have demonstrated that the Model G2TR-[REDACTED] implant has long-term IOP-lowering effects and is also generally well-tolerated by study subjects. These results support the continued evaluation of the implant model in this clinical trial.

2 OBJECTIVE

The study objective is to evaluate the safety of the surgical exchange procedure of Travoprost Intraocular Implant in subjects with a previously implanted Travoprost Intraocular Implant.

3 STUDY DESIGN

This is a prospective, non-randomized, open-label, multi-center, single arm, clinical trial of the safety of the exchange of the Travoprost Intraocular Implant in subjects who were previously implanted with the Travoprost Intraocular Implant in the GC-009 study (1st Cycle). Approximately [REDACTED] [REDACTED] will be enrolled into this study and will be followed through 12 months postoperative.

Screening Procedure:

After providing informed consent, prospective subjects will be evaluated against the Screening criteria. At Visit 1 (Screening), all subjects must meet all entry criteria.

Subjects who qualify at Visit 1 (Screening) may be scheduled for Visit 2 (Operative Exchange Day 0) on a separate day.

The eye previously implanted with a Travoprost Intraocular Implant in the GC-009 study (study eye) will be assessed at Visit 1 (Screening). The subject may then be scheduled for study treatment. Subjects will be treated unilaterally, only the implanted eye (study eye) will go through the study treatment. The fellow eye will be treated outside the parameters of the study per investigator discretion using their standard of care options.

Treatment Procedure:

The Operative and Postoperative scheduled visits are listed in the following table:

Visit Number	Visit Timepoint
2	Operative Exchange Day 0
3	Day 1 Post-Exchange
4	Day 10 Post-Exchange (10 days \pm 3)
5	Week 4 Post-Exchange (28 days \pm 3)
6	Month 3 Post-Exchange (91 days \pm 14)
7	Month 6 Post-Exchange (182 days \pm 30)
8	Month 12 Post-Exchange (365 days \pm 30)

At Visit 2 (Operative Exchange Day 0), subjects will have the first implant which was inserted in Study GC-009 exchanged with a second G2TR-█ implant.

At Visit 1 (Screening), IOP can be measured at any time. At all other scheduled visits, Day 10 Post-Exchange, Week 4 Post-Exchange, Month 3 Post-Exchange, Month 6 Post-Exchange, and Month 12 Post-Exchange), IOP measurements will be taken once daily at the same time as screening \pm 60 minutes. Study follow-up will continue until Visit 8 (Month 12 Post-Exchange), after which subjects will be exited from the study.

3.1 Discussion of Study Design

This prospective, non-randomized, open-label, multi-center, single arm, clinical trial intends to perform an exchange procedure on approximately █ male and female subjects who were previously implanted with the Travoprost Intraocular Implant in the GC-009 study (1st Cycle). All subjects are required to meet eligibility criteria at Visit 1 (Screening). The study objective is to evaluate the safety of the surgical exchange procedure of Travoprost Intraocular Implants in subjects with a previously implanted Travoprost Intraocular Implant. Postoperatively, there are 6 follow-up visits over a 12 month period.

4 STUDY MEASURES

4.1 Efficacy Measures

There are no efficacy measures in this study. IOP is assessed for safety.

4.2 Safety Measures

Ocular safety measures include intra-operative adverse events, post-operative adverse events (TEAEs), IOP, corrected visual acuity, slit lamp biomicroscopy findings, gonioscopy findings, specular microscopy findings, intraocular pressure, ophthalmoscopy findings (including cup-to-disc ratio), and visual field evaluation.

4.3 Other

Operative and Surgical Assessments.

5 MATERIALS

5.1 Study Medications

Subjects will undergo surgery to receive the implants using the test article described below in [Section 5.1.1](#)

5.1.1 TEST ARTICLE: TRAVOPROST INTRAOCULAR IMPLANT MODEL G2TR-[REDACTED]

[figure not shown]

Figure 1. Glaukos Travoprost Intraocular Implant

[figure not shown]
[figure not shown]

Figure 2. Glaukos Travoprost Intraocular Implant and Inserter

Each unique product is packaged in a pouch and outer carton labeled with the study number, unique kit number, and instructions (including storage conditions).

The implant study products will be shipped in a refrigerated container at 2-8°C (36-46°F). The implant study products will be stored at the study site in a refrigerated condition at 2-8°C (36-46°F).

6 METHODS

6.1 Subjects

Approximately 15 centers that enrolled subjects in the GC-009 clinical trial will participate in this study. Approximately 45 subjects who were previously implanted with the Travoprost Intraocular Implant in the GC-009 study (1st Cycle) will have their first implant exchanged with a second Travoprost Intraocular Implant (2nd Cycle). After signing informed consent, prospective subjects will be evaluated to determine whether they meet all other eligibility requirements at Visit 1 (Screening).

6.2 Eligibility Requirements

6.2.1 INCLUSION CRITERIA

6.2.1.1 Visit 1 (Screening) Inclusion Criteria

At the Visit 1 (Screening), all subjects must meet the following criteria:

- 1) Subject status as follows:
 - a. able and willing to attend scheduled follow-up exams for the duration of the study
 - b. able and willing to provide written informed consent on the IRB/IEC-approved Informed Consent Form
- 2) Best spectacle corrected visual acuity of 20/80 or better in each eye.
- 3) Previously implanted with the Travoprost Intraocular Implant in the GC-009 study that is present in the study eye (1st Cycle). Only the eye with the Travoprost Intraocular Implant may be assessed for exchange at Visit 1 (Screening).

All subjects (OAG and OHT) must meet the rest of the following criteria:

- 4) Angle anatomy defined as follows:

a.

6.2.2 EXCLUSION CRITERIA

6.2.2.1 Visit 1 (Screening) Exclusion Criteria

Subjects who meet any of the following criteria in the study eye at Visit 1 (Screening) are not eligible to participate in the study:

1) Glaucoma status as follows:

- a. traumatic, uveitic, neovascular, or angle-closure glaucoma; or glaucoma associated with vascular disorders

b. [REDACTED]

[REDACTED]

[REDACTED]

2) Corneal status as follows:

- a. any active inflammation or edema [REDACTED]

- b. clinically significant dystrophy [REDACTED]

[REDACTED]

e. [REDACTED]

[REDACTED] during the course of the study, that may interfere with IOP measurement reliability

- f. opacities or disorders that would inhibit visualization of the nasal angle.

3) Congenital or traumatic cataract [REDACTED]

4) [REDACTED]

[REDACTED]

[REDACTED]

[REDACTED]

[REDACTED]

6) Other ocular status as follows:

- a. clinically significant sequelae from trauma [REDACTED]
- b. history or chronic ocular inflammatory disease or presence of active ocular inflammation [REDACTED]

7) Fellow eye status as follows:

- a. fellow eye actively enrolled in this trial or any other clinical trial.

8) Subject status as follows:

- a. pregnant or planning to become pregnant during the course of the study
- b. uncontrolled systemic disease (e.g., diabetes, hypertension) that could compromise their participation in the study
- c. current participation in any study, or participation within 30 calendar days of Visit 1 (Screening)
- d. immunodeficiency conditions

e. [REDACTED]

6.2.3 CRITERIA FOR EARLY STUDY EXIT

Subjects may voluntarily withdraw from the study at any time. The investigator may elect to discontinue any subject for reasons unrelated to the study product. Details of a subject's exit from the study should be recorded in the subject's clinical records. Subjects who prematurely discontinue the study may be replaced. Subjects exited after signing the informed consent form and prior to study completion will be handled as follows:

6.2.3.1 Prior to Implantation

Subjects will be ineligible for the study if they fail to meet eligibility criteria ([Section 6.2](#)), if they withdraw consent, or if study enrollment goals have been met.

6.2.3.2 After 2nd Cycle Implantation

Subjects may be exited (discontinued) from the study in the event of a condition that may cause them harm if participation were to be continued. Subjects may also withdraw voluntarily.

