6.5 Post-Treatment Management of IOP and Rescue Medications

7 EXTENT OF EXPOSURE AND TREATMENT COMPLIANCE

All subjects will be implanted with a second Travoprost Intraocular Implant to exchange with the previously implanted first one that will be explanted. All subjects will be followed for the duration of the study.

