9.4 Adverse Events Follow-up

Adverse events will be followed and documented until the time of complete resolution, or resolution with sequelae, or exit from the study with an assessment of the outcome.

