## 4. General Statistical Considerations

Demographic and safety data collected on the case report forms (CRFs) will be displayed in tabulations and data listings. Only data from scheduled visits will be used in tabulations unless otherwise specified. No formal statistical testing will be performed. All data summaries and statistical analyses will be performed using SAS® software, Version 9.4 or higher.

Continuous data will be summarized using the number of observations, mean, standard deviation, median, minimum, and maximum. Continuous data may also be dichotomized, or otherwise split, into clinically meaningful categories and may be further analyzed as categorical data as specified in the individual endpoints.

Categorical data will be summarized using frequency counts and percentages. Unless otherwise stated, subjects with missing visit data will be omitted from both the numerator and denominator of such calculations.

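### Early exit after the exchange ends adverse-event follow-up and visit measures, so by-visit safety summaries can look too favourable if exits are related to ocular harm

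*Protocol*

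**What the plan says.** **Exit.** Protocol 6.2.3.2 says "Subjects may be exited (discontinued) from the study in the event of a condition that may cause them harm". The full condition is "in the event of a condition that may cause them harm if participation were to be continued", so exit is optional and looks forward to the effect of staying in. Section 6.2.3 adds "Subjects who prematurely discontinue the study may be replaced", with no stated limit to exits before surgery.

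**Follow-up.** Protocol Section 7 says "All subjects will be followed for the duration of the study". Section 9.4 ends adverse-event follow-up at resolution, at resolution with sequelae, "or exit from the study with an assessment of the outcome".

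**Analysis.** SAP Section 4 states, for categorical data, that "subjects with missing visit data will be omitted from both the numerator and denominator of such calculations", and limits tabulations to scheduled visits unless otherwise specified. The safety set is everyone who undergoes the exchange (Protocol 8.2, SAP Section 3). SAP 7.1.2 tabulates treatment-emergent events that resulted in discontinuation, serious events and deaths. It also lists events leading to early exit and events leading to implant removal. SAP 5.1 reports early exits with reasons.

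**Size.** Protocol 6.1 gives "Approximately 45 subjects who were previously implanted with the Travoprost Intraocular Implant in the GC-009 study". The synopsis says the number "was determined empirically". No formal testing is planned.

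**The concern.** The intervention is a single operation, and leaving the study does not undo it. Exit only ends observation, yet the readable text offers no status between full participation and exit. A subject who stops protocol procedures therefore also stops contributing safety data.

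Safety is the sole objective. If subjects who exit are more often those whose eye is doing badly, the missing data are informative, and the later tables describe the eyes that did well enough to stay. A reader of the Month 12 column would then see too low a rate of visual or endothelial loss, and could not learn whether an event open at exit later resolved or worsened.

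**Working it through.** The plan states no power, precision, event rate or dropout rate, so there is no figure to reproduce. The check has two parts.

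**1. What exit removes and what it leaves**

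| Item | After early exit |
|---|---|
| Membership of the safety set | Kept |
| Adverse event recorded before exit, with severity, seriousness and relatedness | Kept, over all exchanged subjects (SAP 7.1.2) |
| Outcome of an event open at exit | Status at exit only (Protocol 9.4) |
| Loss of 15 or more letters in corrected acuity | By-visit count only in the readable text, so later visits are lost (SAP 7.1.3.1) |
| Visual field mean deviation | Lost entirely if exit precedes Month 12, the only scheduled post-exchange measurement (SAP 7.1.3.7) |
| Endothelial cell density | Scheduled at Months 3 and 12. A loss measured before exit stays in the overall-study table, but a subject who exits before Month 3 has no scheduled value (SAP 7.1.3.8) |
| Pachymetry and cup-to-disc ratio | Scheduled at Months 3 and 12 only (SAP 7.1.3.9, 7.1.3.4) |

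**2. Size in a by-visit Month 12 table**

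The input N = 45 is from Protocol 6.1. Let e be the number affected at Month 12 under full follow-up, and k the number of these who exit earlier. Both are assumed, and nobody else is taken to be missing.

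- Full follow-up rate = e / N
- Rate shown under SAP Section 4 = (e − k) / (N − k)

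| e | k | Full follow-up | Shown |
|---|---|---|---|
| 3 | 1 | 3/45 = 6.7% | 2/44 = 4.5% |
| 3 | 3 | 3/45 = 6.7% | 0/42 = 0% |
| 5 | 1 | 5/45 = 11.1% | 4/44 = 9.1% |
| 5 | 2 | 5/45 = 11.1% | 3/43 = 7.0% |
| 5 | 3 | 5/45 = 11.1% | 2/42 = 4.8% |
| 5 | 5 | 5/45 = 11.1% | 0/40 = 0% |

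For e = 5 and k = 3, the exact (Clopper-Pearson) 95% intervals are 3.7% to 24.1% under full follow-up and 0.6% to 16.2% as shown. The intervals overlap widely, but the shift is systematic.

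The direction depends on why subjects exit. If 3 unaffected subjects exit instead, the table shows 5/42 = 11.9% against 5/45 = 11.1%, a small error the other way.

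Adverse-event incidence behaves differently. Five events recorded before exit still give 5/45 = 11.1%. If 3 exits are replaced by event-free subjects and all remain in the table, it is 5/48 = 10.4%.

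An any-visit acuity count over the safety set would give 5/45 = 11.1% if all five losses were measured before exit. If the three losses among exited subjects were never measured, it would give 2/45 = 4.4%. Better tabulation therefore recovers what was measured. Only continued collection recovers the rest.

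**The case against.** A reader might infer that the worst outcomes vanish from the safety data. The documents do not support that. Exited subjects remain in the safety set, and the event that led to exit is specifically tabulated and listed. The missing-visit rule does not remove anyone from the adverse-event tables, which count subjects over the safety set and not by visit. Endothelial loss also has an overall-study table, and SAP 7.1.3 includes unscheduled visits in such summaries.

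Nor do the documents show that exits will be caused by harm from the implant or surgery. The trigger is possible harm from continuing, exit is discretionary, and Section 6.2.3 describes investigator-elected discontinuation as being for reasons unrelated to the product. Informative exit is a possibility, not an established fact.

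The conflict with Section 7 can be read as a general sentence qualified by a specific section on early exit, and SAP Section 1 plainly expects some early exits. That makes it a wording conflict and not itself a source of bias. The visit procedures, both schedules and the list of exit reasons cannot be read, so an early-exit examination may exist. Section 9.4 does require an outcome assessment at exit.

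All of this stands, and it limits the point to the post-exit course of open events and to by-visit measures. It does not remove the point. An exit examination would not supply a Month 12 outcome, and the disposition table shows how many left and why without showing which by-visit rates were affected.

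**Conclusion.** The concern holds in this limited form. Early exit ends adverse-event follow-up and later measurements, and the by-visit tables use only the subjects still observed. The acuity-loss count and the visual field summary are most exposed. Endothelial density, pachymetry and cup-to-disc ratio are exposed for subjects who leave before Month 3 or Month 12.

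With about 45 subjects, three informative exits could more than halve a by-visit rate (4.8% against 11.1%), while adverse-event incidence would barely move. The size rests on assumed counts, on every exited subject in the example being affected at Month 12, and on no other missing data. If exits are unrelated to ocular outcome, there is little bias. The study is descriptive, so no test result is at risk. What is at risk is how the later visit columns are read. This should be corrected, but it does not invalidate the safety analysis.

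**What to change.** 1. **Protocol, consistency.** Reconcile Section 7 with Sections 6.2.3, 6.2.3.2 and 9.4, so that one statement says who is followed and for how long. Section 6.3.1 gives a 3-month treatment period while Section 3 has follow-up through Month 12, so the meaning of study duration should be settled at the same time.
2. **Protocol 9.4.** State that, unless consent is withdrawn, adverse events open at early exit are followed for outcome to resolution or Month 12, and that safety data that can still be obtained continue to be collected. The investigator's decision to exit a subject, and which examinations remain suitable, are unchanged.
3. **SAP, by-visit tables.** Beside each denominator, show the number who exited early, with those exited for an adverse event or harm shown separately. State that subjects who are replaced stay in all safety tables.
4. **SAP 7.1.3.1.** Add an overall-study count of subjects with a loss of 15 or more letters at any post-exchange visit, including unscheduled visits, over the safety set. This also counts transient losses, so it belongs beside the by-visit table and does not replace it.

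The cost is protocol and SAP wording, a few follow-up contacts and a few table rows. Some exited subjects will decline or be unable to attend, so some loss of information will remain, but it will be visible.
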